5.1.3 Subject Exclusion Criteria

5.1.3.1 Treatment Groups 1 and 2

The subject must be excluded from participating in the trial if the subject:

1. has an APACHE II score >30 at screening
2. has an infection in which any of the causative pathogens are any of the following:
 - Imipenem-resistant *Acinetobacter* spp.
 - suspected Class B metallo-beta-lactamase-producing bacteria (including NDM-1, IMP or VIM-containing strains)
3. has a concurrent infection that would interfere with evaluation of response to the study antibiotics (IMI/REL or CMS + IMI), including any of the following:
 - endocarditis
 - osteomyelitis
 - meningitis
 - prosthetic joint infection
 - active pulmonary tuberculosis
 - a disseminated fungal infection
4. has received treatment with any form of systemic colistin for > 24 hours within the 72 hours immediately prior to initiation of study therapy.
5. has HABP/VABP caused by an obstructive process, including lung cancer (or other malignancy metastatic to the lungs resulting in pulmonary obstruction) or other known obstruction.
6. has cUTI which meets any of the following:
 - complete obstruction of any portion of the urinary tract (requiring a permanent indwelling urinary catheter or instrumentation)
 - known ileal loop
 - intractable vesico-ureteral reflux
 - presence of indwelling urinary catheter which cannot be removed at study entry

NOTE: All indwelling urinary catheters must be removed prior to the start of IV therapy. Unless medically necessary, it is recommended that an indwelling urinary catheter not be reinserted while on IV study therapy.

7. has a history of serious allergy, hypersensitivity (e.g., anaphylaxis), or any serious reaction to any of the following:

- any carbapenem, cephalosporin, penicillin, or other β -lactam agent
- colistimethate sodium (colistin) or to polymyxin B
- other β -lactamase inhibitors (e.g., tazobactam, sulbactam, clavulanic acid, avibactam)

NOTE: Subjects with a history of mild rash to penicillins or other β -lactams may be enrolled and closely monitored.

8. is a female who is pregnant or is expecting to conceive (or is a male partner of a female who is expecting to conceive), is breastfeeding, or plans to breastfeed prior to completion of the study.

9. has any of the following medical conditions at screening:

- history of a seizure disorder (requiring ongoing treatment with anti-convulsive therapy or prior treatment with anti-convulsive therapy within the last 3 years)
- myasthenia gravis
- porphyria
- cystic fibrosis
- granulomatous disease

10. is anticipated to be treated with any of the following medications during the course of study therapy:

- valproic acid or divalproex sodium (or has used valproic acid or divalproex sodium in the 2 weeks prior to screening)
- concomitant IV, oral, or inhaled antimicrobial agents with known coverage of Gram-negative bacteria of interest (i.e., Enterobacteriaceae, *Pseudomonas* spp. and Gram-negative anaerobic bacilli), in addition to those designated in the study treatment groups.

NOTE: Use of IV vancomycin, IV daptomycin, or IV linezolid to treat confirmed or suspected methicillin-resistant *S. aureus* (MRSA) infection, use of IV linezolid or IV daptomycin to treat confirmed or suspected vancomycin-resistant *Enterococcus* spp. (VRE) infection, or use of trimethoprim-sulfamethoxazole (TMP/SMX) or other standard-of-care agent for prophylaxis of opportunistic infection (e.g., *Pneumocystis jiroveci* infection) in immunocompromised subjects is allowed. Daptomycin is not indicated for the treatment of HABP/VABP (Refer to Section 5.5).

11. has an estimated or actual creatinine clearance of less than 15 mL/min at screening based on the findings of local laboratory values. Creatinine clearance in mL/min may be calculated from serum creatinine concentration by the Cockcroft-Gault (C-G) equation:

$$\text{Creatinine clearance (Males)} = \frac{(\text{weight in kg}) \times (140 \text{ minus age})}{(72) \times (\text{creatinine in mg/dL})}$$

Creatinine clearance (Females) = 0.85 X the value obtained using the formula above

12. is currently undergoing hemodialysis or peritoneal dialysis.
13. has a history or current evidence of any condition, therapy, laboratory abnormality, or other circumstance that, in the opinion of the investigator, might confound the results of the study, interfere with the subject's participation for the full duration of the study, or pose additional risk in administering the study drugs to the subject.
14. is currently participating in, or has participated in, any other clinical study involving the administration of investigational or experimental medication (not licensed by regulatory agencies) at the time of the presentation or during the previous 30 days prior to screening or is anticipated to participate in such a clinical study during the course of this trial.
15. is or has an immediate family member (spouse or children) who is investigational site or sponsor staff directly involved with this trial.
16. has previously participated in this study at any time.

5.1.3.2 Open-Label, Treatment Group 3

The subject must be excluded from participating in the trial if the subject:

1. has an infection in which any of the causative pathogens are any of the following:
 - Imipenem-resistant *Acinetobacter* spp.
 - suspected Class B metallo-beta-lactamase-producing bacteria (including NDM-1, IMP or VIM-containing strains)
2. has a concurrent infection that would interfere with evaluation of response to IMI/REL, including any of the following:
 - endocarditis
 - osteomyelitis
 - meningitis
 - prosthetic joint infection
 - a disseminated fungal infection
 - active pulmonary tuberculosis

3. has HABP/VABP caused by an obstructive process, including lung cancer (or other malignancy metastatic to the lungs resulting in pulmonary obstruction) or other known obstruction.
4. has cUTI which meets any of the following:
 - complete obstruction of any portion of the urinary tract (requiring a permanent indwelling urinary catheter or instrumentation)
 - known ileal loop
 - intractable vesico-uretral reflux
 - presence of indwelling urinary catheter which cannot be removed at study entry

NOTE: All indwelling urinary catheters must be removed prior to the start of IV therapy. Unless medically necessary, it is recommended that an indwelling urinary catheter not be reinserted while on IV study therapy.

5. has a history of serious allergy, hypersensitivity (e.g., anaphylaxis), or any serious reaction to any of the following:
 - Any carbapenem, cephalosporin, penicillin, or other β -lactam agent
 - other β -lactamase inhibitors (e.g., tazobactam, sulbactam, clavulanic acid, avibactam)

NOTE: Subjects with a history of mild rash to penicillins or other β -lactams may be enrolled and closely monitored.

6. is a female who is pregnant or is expecting to conceive (or is a male partner of a female who is expecting to conceive), is breastfeeding, or plans to breastfeed prior to completion of the study.
7. has a history of a seizure disorder (requiring ongoing treatment with anti-convulsive therapy or prior treatment with anti-convulsive therapy within the last 3 years)
8. is anticipated to be treated with any of the following medications during the course of study therapy:
 - valproic acid or divalproex sodium (or has used valproic acid or divalproex sodium in the 2 weeks prior to screening)
 - concomitant IV, oral, or inhaled antimicrobial treatments with known coverage of Gram-negative bacteria of interest (i.e., Enterobacteriaceae, *Pseudomonas* spp. and Gram-negative anaerobic bacilli) in addition to those designated in the study treatment groups (prior use of antimicrobial agents is permitted).

NOTE: Use of IV vancomycin, IV daptomycin, or IV linezolid to treat confirmed or suspected methicillin-resistant *S. aureus* (MRSA) infection, use of IV linezolid or IV daptomycin to treat confirmed or suspected vancomycin-resistant *Enterococcus* spp. (VRE) infection, or use of TMP/SMX or other standard-of-care agent for prophylaxis of opportunistic infection (e.g., *P. jiroveci* infection) in immunocompromised subjects is allowed. Daptomycin is not indicated for the treatment of HABP/VABP (Refer to Section 5.5).

9. has an estimated or actual creatinine clearance of less than 15 mL/min at screening based on the findings of local laboratory values. Creatinine clearance in mL/min may be calculated from serum creatinine concentration by the C-G equation:

$$\text{Creatinine clearance (Males)} = \frac{(\text{weight in kg}) \times (140 \text{ minus age})}{(72) \times (\text{creatinine in mg/dL})}$$

Creatinine clearance (Females) = 0.85 X the value obtained using the formula above

10. is currently undergoing hemodialysis or peritoneal dialysis.
11. has a history or current evidence of any condition, therapy, laboratory abnormality, or other circumstance that, in the opinion of the investigator, might confound the results of the study, interfere with the subject's participation for the full duration of the study, or pose additional risk in administering the study drugs to the subject.
12. is currently participating in, or has participated in, any other clinical study involving the administration of investigational or experimental medication (not licensed by regulatory agencies) at the time of the presentation or during the previous 30 days prior to screening or is anticipated to participate in such a clinical study during the course of this trial.
13. is or has an immediate family member (spouse or children) who is investigational site or sponsor staff directly involved with this trial.
14. has previously participated in this study at any time

5.2 Trial Treatment(s)

The treatments to be used in this trial are outlined below in [Table 10](#).

Table 10 Trial Treatments

Drug	Dose/Potency ^b	Dose Frequency	Route of Administration	Regimen/Treatment Period ^c	Use
Treatment Group 1 (N = 36) or Treatment Group 3					
Imipenem/cilastatin/relebactam (IMI/REL) ^a	Imipenem: 500 mg Relebactam: 250 mg	Every 6 hours	IV	5 or 7 to 21 days	Experimental
Placebo for CMS (diluent for CMS as directed in the Pharmacy Manual)	N/A	Loading dose followed after 12 hours by maintenance dose every 12 hours	IV	5 or 7 to 21 days	Placebo-control
Treatment Group 2 (N = 18)					
Colistin as colistimethate sodium (CMS)	Total maximum daily maintenance dose: 300 mg CBA ^d	Loading dose followed after 12 hours by maintenance dose every 12 hours	IV	5 or 7 to 21 days	Active-comparator
Imipenem/cilastatin (IMI)	Imipenem: 500 mg	Every 6 hours	IV	5 or 7 to 21 days	Active-comparator
CBA: Colistin base activity (300 mg CBA corresponds to approximately 720 mg CMS or ~9 million IU) ^a IMI/REL will be provided combined in a single vial. ^b Adjustments to dosage of IMI/REL, IMI and CMS may be required. Dose adjustment for IMI/REL and IMI are required for subjects with renal insufficiency (Reference Table 11 in Section 5.2.1.1). Dose adjustment for CMS dose in subjects with renal insufficiency is also required (Reference Table 12 in Section 5.2.1.1). ^c IV study therapy should be administered for a minimum of 120 hours (5 full days) for subjects with cIAI or cUTI or 168 hours (7 full days) for subjects with HABP/VABP. The corresponding number of doses required is described in Section 7.1.5.2. The total duration of IV study therapy should not exceed 21 days. Duration of study therapy longer than 21 days must be approved the Sponsor. ^d Subjects who require a loading dose of CMS (Reference Table 12 in Section 5.2.1.1) will receive >300 mg CBA during the first 24 hours of study therapy.					

Trial therapy should begin on the same day as IVRS assignment of therapy for all subjects (i.e., randomization for Treatment Groups 1 and 2 or allocation assignment for Treatment Group 3). The first dose of prescribed study therapy should be administered at the Day 1 visit. The Unblinded Study Pharmacist (or qualified designee) will contact the interactive voice response system/integrated web response system (IVRS/IWRS) for assignment of the study therapy to be administered. Sites should not call IVRS/IWRS for drug administration until the subject has met all entry criteria for the study and ready to be randomized. All subjects in each treatment group will receive a minimum of either 5 days (cIAI, cUTI) or 7 days (HABP/VABP) up to a maximum of 21 days of intravenous (IV) study therapy. Duration of study therapy longer than 21 days must be approved the Sponsor.

Detailed dosing guidelines, including dose selection and timing of dose administration, are outlined in Section 5.2.1.1 and Section 5.2.2, respectively.

5.2.1 Dose Selection/Modification

5.2.1.1 Dose Selection

For subjects with renal insufficiency, the dose of IMI/REL (in Treatment Group 1 or Treatment Group 3) and IMI (in Treatment Group 2) must be adjusted based upon the degree of renal function impairment, as determined by the estimated or actual creatinine clearance. It is important to note that if a change in the subject's creatinine clearance during IV study therapy could result in dosage adjustments at any time during IV therapy. Dose adjustments according to creatinine clearance are included in [Table 11](#).

Creatinine clearance in mL/min may be calculated from serum creatinine concentration by the C-G equation:

$$\text{Creatinine clearance (Males)} = \frac{(\text{weight in kg}) \times (140 - \text{minus age})}{(72) \times (\text{creatinine in mg/dL})}$$

$$\text{Creatinine clearance (Females)} = 0.85 \times \text{the value obtained using the formula above}$$

Subjects in Treatment Group 2 will also receive colistin as CMS. Upon randomization and initiation of IV study therapy, the dosage of the first dose of CMS for Treatment Group 2 subjects will depend on the subject's previous history of receipt of colistin within the 72 hours prior to entry in the study. Specifically, if a loading dose >200mg CBA (corresponding to ~ 470 mg CMS or 5.9 million IU) was administered prior to entry, the subject should begin maintenance doses described in [Table 12](#) upon initiation of IV study therapy. It should be noted that a loading dose is defined based on the dosage of any individual dose(s) administered rather than the total dosage over a series of doses in a subject who has received >1 dose prior to entry. If the subject has not received a loading dose (i.e., an individual dose \geq 200 mg CBA) prior to study entry, the protocol-specified loading dose of CMS of 300 mg CBA (corresponding to ~ 720 mg CMS or ~9 million IU) should be provided as shown in [Table 12](#), regardless of the dosage previously administered.

Twelve (12) hours after the initial loading dose, maintenance dosing will begin and then continue every 12 hours (q12h) thereafter. The maintenance dose of CMS will be based on creatinine clearance according to [Table 12](#). Creatinine clearance may be calculated from serum creatinine concentration by the equation previously provided. It is important to note that a change in the subject's creatinine clearance during IV study therapy could result in dosage adjustments at any time during IV therapy.

Subjects assigned to Treatment Group 1 will receive a matching placebo for CMS on the same schedule as subjects in Treatment Group 2 (first dose upon initiation of therapy followed by q12h maintenance doses beginning 12 hours later). Since Treatment Group 3 is open-label, no placebo will be administered to subjects enrolled into this Treatment Group.

Table 11 Administration Dosage of IMI/REL and IMI According to Renal Function

Creatinine Clearance (mL/min)	IMI/REL^a	IMI
≥ 90	500/250 mg q6h	500 mg q6h
< 90 to ≥ 60	400/200 mg q6h	400 mg q6h
< 60 to ≥ 30	300/150 mg q6h	300 mg q6h
< 30 to ≥ 15	200/100 mg q6h	200 mg q6h
^a IMI/REL is provided as a single vial in a fixed-dose combination; therefore, the dose for each component will be adjusted equally during preparation. For example, a Treatment Group 1 subject who has a creatinine clearance of 50 mL/min should receive a 150 mg q6h dose of REL according to the table. Since the dose is reduced by 50% during preparation, the total mg of IMI would also be reduced by 50%, thus resulting in a 300 mg q6h dose of IMI.		

Table 12 Administration Dosage of Loading and Daily Maintenance Doses of CMS According to Renal Function

Creatinine Clearance (mL/min)	Loading Dose^a	Maintenance Dose^b
≥ 90	300 mg CBA (~720 mg CMS or ~9 million IU)	150 mg CBA (~360 mg CMS or ~4.5 million IU)
< 90 to ≥ 60		150 mg CBA (~360 mg CMS or ~4.5 million IU)
< 60 to ≥ 30		115 mg CBA (~270 mg CMS or ~3.4 million IU)
< 30 to ≥ 15		75 mg CBA (~180 mg CMS or ~2.3 million IU)
CMS = colistimethate sodium; CBA = colistin base activity.		
^a If a loading dose ≥ 200 mg CBA (~470 mg CMS or ~5.9 million IU) was administered prior to study entry, the subject should begin maintenance doses upon initiation of IV study therapy. If the subject has not previously received a loading dose, a loading dose should be provided as described, regardless of the dosage previously administered.		
^b With the exceptions noted in footnote a, the maintenance dose will be administered 12 hours following administration of the loading dose and will be administered every 12 hours thereafter.		

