As previously discussed, REL, imipenem, and CIL are primarily renally excreted, with similar increases observed for each analyte in a Phase I renal insufficiency study (PN005). Thus, dose adjustments can be made in the same proportion for both REL and IMI, and all can be dosed in a fixed ratio. IMI and REL will be provided together in a single vial as a fixed-dose combination product in this study (IMI/REL). Dose adjustment is required in subjects with renal impairment. Depending on the individual subject's renal function (as determined by actual or estimated creatinine clearance), the total daily dose of IMI/REL may be adjusted. The IMI package circular also includes reduced daily doses for patients with lower body weight. The total daily dose for IMI-containing therapy (IMI/REL and IMI) for subjects in this study will not be adjusted for weight. This approach is consistent with general clinical practice and other recent clinical trials using IMI as a comparator. For example, clinical trials for HABP/VABP published since 2006 have administered IMI at standard dosages without an adjustment for weight. Efficacy rates in these trials have ranged from ~60 to 80% without significant toxicity [42 – 45]. The few published clinical trials in which IMI dosage was adjusted for weight describe similar efficacy and safety [46, 47]. Furthermore, weight is already a component of calculated creatinine clearance, used for determination of

renal function and need for dose adjustment, thus raising the theoretical concern of under-dosing in subjects with low body weight. Population PK-based simulations were conducted to evaluate the impact of removal of weight-based adjustments for IMI. Results of these simulations indicate that in individuals of lower weight, exposures of IMI/REL are significantly lower than those in higher weight ranges when doses are adjusted based on weight, and are supportive of dose adjustments based solely on renal function, as has been described above in clinical practice. Specifically, simulation results indicate that in subjects with normal renal function, the dose of 250 mg REL and 500 mg IMI is appropriate. For subjects with mild renal insufficiency, the dose should be reduced to 200 mg REL and 400 mg IMI, for moderate renal insufficiency 150 mg REL and 300 mg IMI, and for severe renal insufficiency 100 mg REL and 200 mg IMI. The specific dosing guidelines are included in Section 5.2.1.1 ([Table 11](#)).

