9.0 LABELING, PACKAGING, STORAGE AND RETURN OF CLINICAL SUPPLIES

9.1 Investigational Product

The investigator shall take responsibility for and shall take all steps to maintain appropriate records and ensure appropriate supply, storage, handling, distribution and usage of investigational product in accordance with the protocol and any applicable laws and regulations.

Clinical Supplies will be provided by the Sponsor as summarized in Table 20.

Table 20 Product Descriptions

Product Name & Potency	Dosage Form
MK-7655A, MK-7655 250 mg (Anhydrous Equivalent), IMIPENEM 500 mg (Anhydrous Equivalent) and CILASTATIN EQUIVALENT 500 mg	Powder for Constitution
IMIPENEM 500 mg (Anhydrous Equivalent) and CILASTATIN EQUIVALENT 500 mg (PRIMAXIN I.V.)	Powder for Reconstitution
Colistimethate Sodium for Injection (Equivalent to 150 mg Colistin)	Lyophilized Powder for I.V. Injection

All other supplies not indicated in [Table 20](#) above will be provided centrally by the Sponsor or locally by the trial site, subsidiary or designee, depending on local country operational or regulatory requirements.

For any commercially available product that is provided by the trial site, subsidiary or designee every attempt will be made to source these supplies from a single lot/batch number. The trial site will be responsible for recording the lot number, manufacturer and expiry date of any locally purchased product.

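### Table 11 footnote a calls a 40% dose reduction a 50% reduction, and the prior-colistin loading-dose cut-off is strict in one sentence but inclusive elsewhere

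*Combined protocol and SAP*

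**What the plan says.** **IMI/REL dose by renal function.** Table 11 (Section 5.2.1.1) has four creatinine-clearance rows, from 500/250 mg q6h (IMI/REL) at 90 mL/min or more down to 200/100 mg q6h at 15 to below 30 mL/min. The row for 30 to below 60 mL/min is 300/150 mg q6h. Footnote a is marked on the IMI/REL column only and explains how a fixed-ratio vial is adjusted. Its example subject has a "creatinine clearance of 50 mL/min should receive a 150 mg q6h dose of REL according to the table". It continues "Since the dose is reduced by 50% during preparation, the total mg of IMI would also be reduced by 50" per cent, "thus resulting in a 300 mg q6h dose of IMI". Section 4.2.2.1 gives the same amounts: "for moderate renal insufficiency 150 mg REL and 300 mg IMI".

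**Prior colistin and the first CMS dose.** Section 5.2.1.1 says that subjects in Treatment Group 2 start directly on maintenance "if a loading dose >200mg CBA (corresponding to ~ 470 mg CMS or 5.9 million IU) was administered prior to entry". Two sentences later, the same paragraph describes a loading dose as an individual dose of 200 mg CBA or more. Table 12 footnote a is also inclusive: "If a loading dose ≥ 200 mg CBA". Section 5.2.2 makes the 300 mg CBA loading dose the default, except in certain subjects with prior colistin as described in Section 5.2.1.1.

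**The concern.** A worked example under a dosing table is there to show a preparer how to do the calculation. Here the percentage in the example does not produce the amounts in the example. The study bags are prepared and sleeved by an unblinded pharmacist or designee, and the staff who administer them to randomized subjects are blinded (Sections 4.2.2.4 and 5.2.3). A slip at preparation would therefore be hard for others to see. Because the footnote sits on the IMI/REL column, any slip it caused would fall on the test drug and not on IMI in the comparator arm.

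For CMS, the two cut-offs lead to different first doses for one prior dose level. Section 7.2.1 defines a CMS overdose as a daily total above the Table 12 doses, reportable within 24 hours. For a subject at exactly 200 mg, whether a 300 mg CBA first dose is protocol-specified or an overdose therefore depends on which sentence is read.

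**Working it through.** **1. The percentage in Table 11 footnote a**

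Inputs: the full dose is 500 mg IMI / 250 mg REL (Table 11, first row), which is also the vial content (Section 9.1, Table 20). The example dose is 300 mg IMI / 150 mg REL (Table 11, third row; footnote a; Section 4.2.2.1). The stated reduction is 50% for both components (footnote a).

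Formula: reduction = 1 − (row dose / full dose).

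| Creatinine clearance (mL/min) | IMI/REL (mg) | IMI share | REL share | Reduction |
|---|---|---|---|---|
| ≥90 | 500/250 | 1.00 | 1.00 | 0% |
| 60 to <90 | 400/200 | 0.80 | 0.80 | 20% |
| 30 to <60 | 300/150 | 0.60 | 0.60 | 40% |
| 15 to <30 | 200/100 | 0.40 | 0.40 | 60% |

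The stated 50% is not reproduced in any row. Other possible bases were tried:

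- Daily totals: 1200/2000 mg IMI = 0.60 and 600/1000 mg REL = 0.60, still a 40% reduction.
- Against the adjacent 400/200 mg row: 1 − 300/400 = 25%.
- Starting dose needed for a 50% reduction to end at 300/150 mg: 300/0.5 = 600 mg IMI and 150/0.5 = 300 mg REL. The documents contain no such dose.
- A 50% reduction applied to the vial: 500 × 0.5 = 250 mg IMI and 250 × 0.5 = 125 mg REL. This is not a row of Table 11.

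Gap between following the percentage and following the row: 1 − 250/300 = 1 − 125/150 = 16.7% per dose.

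**2. The prior-colistin cut-off**

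First, the statements refer to the same threshold. Using the Table 1 potency of 0.424 mg CBA per mg CMS and 12,500 IU per mg CMS, 200/0.424 = 472 mg CMS, and 472 × 12,500 = 5.9 million IU. These match the equivalents of about 470 mg and 5.9 million IU given in Section 5.2.1.1 and Table 12.

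Both wordings applied to a prior individual dose:

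| Prior dose (mg CBA) | Strict wording (above 200) | Inclusive wording (200 or more) |
|---|---|---|
| 199 | not exempt: loading dose | loading dose |
| 200 | not exempt: loading dose by the Section 5.2.2 default | maintenance |
| 201 | maintenance | maintenance |

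The wordings part only at exactly 200 mg. There the first dose is 300 mg CBA on one reading, and 150, 115 or 75 mg CBA on the other, depending on the Table 12 row.

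Whether a real prior dose lands on 200 mg depends on the conversion used. With 9 million IU = 300 mg CBA (Table 1), 6 million IU gives 6 × 300/9 = 200 mg. With the 0.424 potency, 6,000,000/12,500 × 0.424 = 203.5 mg. The documents do not say how often such a dose occurs.

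**The case against.** The best defence is that the milligram instructions do not conflict. The footnote starts at the Table 11 dose of REL and ends at the Table 11 dose of IMI, and Section 4.2.2.1 repeats both. Sections 5.2.2 and 7.1.2.1 send the reader to Tables 11 and 12 for the dosage. Under Section 6.0, creatinine clearance goes to IVRS daily to support dose determination. Preparation detail sits in a Pharmacy Manual that is not among the documents. A preparer would have to set all of this aside to act on the percentage. This stands, and it limits the consequence. It does not make the percentage agree with the amounts.

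Three stronger inferences are tempting. A reader might conclude that all subjects with clearance of 30 to below 60 mL/min would be dosed 16.7% away from the table. The documents do not support that: the figure applies only where a preparer prefers the percentage to the row, and no passage states 250/125 mg as a dose. A reader might also expect exposure-response or nephrotoxicity results to be blurred. Nothing in the documents shows that any dose would be prepared from the percentage, so this is speculation. Finally, a reader might call the cut-off a broad dosing conflict. It concerns the choice of first CMS dose, not preparation. It touches only Treatment Group 2 (about 18 subjects), and within it only those with a prior dose of exactly 200 mg CBA. Exclusion criterion 4 already bars more than 24 hours of systemic colistin in the preceding 72 hours.

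A ≥ sign can also be lost when a PDF is converted to text, so the strict sign should be confirmed against the approved protocol. The 50% figure, stated twice in one sentence, is not open to that doubt.

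**Conclusion.** Both discrepancies hold as internal inconsistencies of limited reach. In footnote a, a stated 50% reduction accompanies amounts that are a 40% reduction. The possible dose difference is 16.7%, conditional on someone following the percentage over the table. The cut-off wording gives two first-dose instructions at one value, exactly 200 mg CBA, subject to confirming the printed sign.

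The conclusion rests on the full dose and vial both being 500/250 mg, as the protocol states. The Pharmacy Manual and the IVRS programming were not available, and either may already resolve both points in practice. Which dose or cut-off is intended is for the sponsor to state. Correcting the text offers a small safety benefit.

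**What to change.** - Reconcile the percentage in Table 11 footnote a with the Table 11 row and with the amounts in the footnote itself.
- Reconcile the cut-off wording within Section 5.2.1.1 and with Table 12 footnote a, so that a prior individual dose of exactly 200 mg CBA has one instruction.
- Check both points against the Pharmacy Manual and the IVRS dose logic, so that all sources agree.
- If subjects are still being dosed, notify the unblinded pharmacists and their designees.

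The cost is two wording corrections, one cross-check and, if needed, a short site letter. No analysis, population or sample-size text changes.
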